Although specific mechanisms contributing to changes in the arginine metabolome during VOE are unknown, hemolysis is unlikely to play a major role at least initially, as straightforward VOE is not typically associated with a lower than baseline hemoglobin (Hb), although our data shows a significant Hb drop within the first 24 hours after admission (1). A ≥1 gram drop in baseline Hb at presentation for pain can be a red-flag for impending ACS (54, 55). Our early studies revealed a falling arginine level reaching a nadir within 24 hours of a positive CXR (**Fig 5A**), days into the VOE admission, a pattern that differed from uncomplicated VOE (**Fig 2B**) (4). Dysregulation of arginine metabolism appears to be different in VOE vs. ACS (4), & mechanisms for arginine consumption in VOE should be sought out in future arginine trials since it may impact response to arginine therapy. Insight into these paradigms may allow us to develop novel targeted therapies. L-arginine supplementation inhibits the red cell Gardos channels (12), reduces red cell density (12), improves perfusion, and reduces lung injury, microvascular vaso-occlusion and mortality (14-17). Arginine also increases erythrocyte glutathione levels in both mouse (15) and human trials (18), and may down-regulate inflammatory pathways (19). However, none of these mechanisms of action have been studied during VOE in children with SCD. In addition, arginine is a key substrate in creatine synthesis, an important metabolic pathway not yet sufficiently studied in SCD that may be impacted by an arginine- deficient state. Although the role of NO in SCD has become controversial (56, 57), these studies demonstrate that the mechanistic impact of arginine goes beyond NO. We speculate, however, that improved NO bioavailability with arginine therapy may also be a contributing factor in children with vaso-occlusive pain.

Based on preliminary pharmacokinetic studies (5, 49), peak plasma arginine concentration after oral arginine (0.1 g/kg) is significantly higher during SCD steady-state compared to VOE (Fig 5B), although levels are similar by 4 hours. Normal controls reach a peak arginine level between 1-2 hours that is maintained at 4 hours, & does not trend down as in SCD (5). Accelerated arginine metabolism or consumption occurs during VOE compared to steady-state despite the same oral arginine dose given.

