Once informed consent is obtained, eligible children and adolescents age 3-21 years will be randomized to one of three study arms: Standard L-arginine dose (100 mg/kg IV TID), one-time L-arginine loading dose (200 mg/kg IV) + standard dose (100 mg/kg IV TID), or placebo (normal saline 1-2 ml/kg IV TID) up to a maximum of 7 days (21 doses) or until discharge, whichever comes first. The maximum loading dose of IV L-arginine will be 20 grams, with a standard dose maximum of 10 gms IV TID. A total of 114 patients will be treated/randomized in this protocol, 38 in each arm. Up to 150 patients may be enrolled, to account for potential screen failures and withdrawals. **Patients must be randomized within 24 hours of receiving their initial parenteral opioid in the ED or clinic/day hospital.** Even though a 24-hr window is established for feasibility, the ideal goal is to randomize and deliver study drug within 2-4 hours in the ED or clinic/day hospital. The average time to study drug delivery in the original [name] Arginine study was 20.4 ± 11 hours (1). Although this original study was not sufficiently powered to detect a decreased length of hospital stay (LOS), the trending decrease by 17 hours is a clinically relevant improvement for patients and their families. A standardized treatment and monitoring protocol for VOE utilized by Emory/Children's Healthcare of Atlanta mutually agreed upon by both the ED and department of hematology will be followed. Pain scores (0-10 scale or FACES as appropriate) will be obtained at presentation to the acute care setting for pain prior to study drug administration and at least TID until discharge. If the patient is discharged from the ED or day hospital/clinic without a hospital admission, a discharge pain score will also be obtained. A discharge blood draw will be obtained whenever possible for those discharged from the ED but will be limited to research labs targeting the arginine metabolome (plasma and erythrocyte amino acids, arginase activity, NO_x and exhaled NO). Information on hydroxyurea use (HU) will be obtained. Randomization will be stratified for HU use to minimize potential confounding effects of HU use. Patients,

physicians, and staff involved in patient care will be blinded as to whether each patient receives arginine vs. placebo.

Patients already participating in the clinical trial may not be enrolled more than once.

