Pain Scores: Pain associated with VOE will be measured on a numeric pain rating scale of 0-10, with the ends representing the extreme limits of "no-pain" (0) and "worst pain" (10), or the FACES pain rating scale when appropriate. Pain scores will be obtained at presentation to the acute care setting for pain prior to study drug administration and at least TID daily, until discharge and at time of discharge.

Specific Aim 2: Safety monitoring

To monitor for potential toxicities associated with a loading dose & repeated administration of IV L-arginine.

Vital signs including blood pressure, hemoglobin, liver and renal function testing will be obtained at the same time as the study blood draw for research labs. Rates of acute chest syndrome, blood transfusion, clinical deterioration, need for intensive care and hospital/ED returns within 72 hours and 30 days will be monitored in all enrolled patients and compared between study arms.

Primary Outcome Measure: *The primary outcome measure is total parenteral opioid use (morphine equivalents mg/kg) calculated from the initial dose of study drug, throughout the ED and/or hospital stay in the arginine arms compared to placebo.*

Secondary Outcome Measures:

Clinical Outcomes

1. Length of hospital stay from study drug delivery to discharge (time of discharge order)
2. Time to VOE resolution after study drug delivery
3. Pain scores at presentation vs. discharge
4. Pain score over time
5. Length of ED stay (time of ED triage to discharge or admission order)
6. ED discharge rate
7. Total opioid dose (mg/kg) in the first 8 hours after study drug delivery
8. Number of study drug doses
9. Rate of acute chest syndrome (not present before randomization)
10. Rate of blood transfusion
11. Change in oxygen saturation and use of supplemental oxygen during admission. PROMIS pediatric Pain and Fatigue short forms (daily for up to 1st 7 days and then on day of discharge: collaboration with [name]/[name])
12. Symptoms questionnaire
13. 72-hour returns and 30-day return visits to the ED or in-patient hospitalizations
14. Diffusion correlation spectroscopy

Study Labs: Clinical, Research and Safety Monitoring

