- If CMP and creatinine levels were normal enough to not meet exclusion criteria in the past 12 months, the patient can receive the first dose of study drug and the CMP and creatinine labs reviewed when available.
- Patients with a CMP after randomization that meet exclusion criteria will have study drug stopped for toxicity monitoring. With an intention-to-treat analysis, these patients will remain on study. Blood analysis and exhaled NO_x measurements will continue per protocol, but arginine/placebo supplementation will be terminated.

Administration of Analgesics to Study Patients

Patient Controlled Analgesia (PCA) devices will be used in admitted patients whenever possible according to standard practice at CHOA. Intravenous ketorolac, oral NSAIDS and oral opioids with acetaminophen may be used in addition to parenteral opioids. Intranasal fentanyl may be administered at presentation in the ED per protocol. Dosing of the PCA will follow a standard protocol of pain management established by the Aflac sickle cell center.

Monitoring During Study

Patients will be identified from the over 1400 ED SCD patient visits/year for VOE in children followed by the staff at the Aflac Sickle Cell Center of CHOA/Emory University School of Medical. They will be examined daily by the clinical team and will undergo routine vital signs including blood pressure per clinical protocol. A chart review will be performed, and pertinent data extracted. A pain score will be obtained and recorded daily (at least 3 times a day, once per shift) and at time of discharge. Standard of care pain scores will be utilized. A symptom questionnaire to assess for potential side effects of arginine will be completed daily by the study coordinator (see appendix). Information for the symptom's questionnaire evaluating for potential adverse events should be obtained by direct questioning of the patient/family in addition to the medical record. Use of parenteral narcotics will be documented every shift by nursing staff per standard protocol and will include narcotics delivered by the PCA device as well as any additional intravenous, intranasal and/or oral opioids used. Data on total daily opioid use will be collected by study team coordinator.

Laboratory monitoring will be undertaken according to the schedule below:

	DAY 0	DAY 1	Day 7/Discharge*
CBC with retic count (SOC)	X	X	X
Comprehensive metabolic panel	X	X	X
Urinalysis for protein (urine to Brown lab)	X	X	X
BHCG (girls > 12 yrs)	X		

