RESEARCH LABS	X		X
See Specific Aim 3			
Arginine Metabolome	X	X	X

Total research Blood draw/day < 20 cc (less than 2 tablespoons)

*Day 0 pre-study drug delivery and Day 1 is the first day >12 hours after study drug initiation. If routine daily labs occur within < 12 hours of the first study drug dose, day 1 labs may be rescheduled to the following day. *Discharge bloodwork will be obtained on Day 7 of arginine therapy for prolonged admissions AND day of discharge. Day 7 is the day that the last dose # 21 will be given for patients who have not yet been discharged. Discharge labs may be obtained with routine daily blood draw whenever possible and may be drawn on days when the research and clinical team suspect the patient may be discharged, to avoid multiple venipuncture. In the event the patient is not discharged on that date, discharge labs should be drawn again prior to discharge. Tests may be run on discarded samples saved up to 72 hours if needed.*

Toxicity Monitoring/ Study Drug Stopping Rules

Patients will be removed from the study if they meet the following criteria:

- 1) Neurological dysfunction or development of stroke while on protocol
- 2) Increase in SGPT to > 6X ULN value
- 3) Increase in creatinine to >3X value at study entry or >2.0
- 4) Allergic reaction to study medication
- 5) Patient's request
- 6) Acidosis with CO₂ ≤ 16
- 7) Hypotension requiring treatment with clinical intervention
- 8) Concern by study team and sickle cell clinical team that a serious adverse event is related to study drug

Data from patients removed from the study will be collected and analyzed for potential side effects or toxicities of arginine. Blood analysis and exhaled NO_x measurements will continue per protocol, but arginine/placebo supplementation will be terminated. Patients who ALT values increased >6X ULN, the ALT will be monitored daily with a study CMP until the values are no longer increasing, then once weekly or until patient is clinically stable for discharge, whichever is first.

ACS severity definition

ACS is defined as a new pulmonary infiltrate associated with fever, chest pain or respiratory symptoms. ACS is a clinical diagnosis and will be determined based on discharge diagnosis by the hematology team. Severity of ACS for the purposes of this study will be defined as mild, moderate or severe based on the

criteria below, based on a definition created for other trials in SCD.

- **Mild:** +CXR with no oxygen use or transfusion required

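### Acute chest syndrome, transfusion, deterioration and intensive care are compared between arms with no common observation window; if arginine shortens the stay, in-stay rates would be modestly biased in its favour

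*Combined protocol and SAP*

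**What the plan says.** Under Specific Aim 2: Safety monitoring, the plan says: "Rates of acute chest syndrome, blood transfusion, clinical deterioration, need for intensive care and hospital/ED returns within 72 hours and 30 days will be monitored", and that this will be done "in all enrolled patients and compared between study arms". Only the return visits carry a time limit.

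The Secondary Outcome Measures repeat two of these endpoints. Item 9 is "Rate of acute chest syndrome (not present before randomization"), which gives a start but no end. Item 10, transfusion, gives neither. Item 13 lists "72-hour returns and 30-day return visits to the ED or in-patient hospitalizations" as a separate outcome.

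Under ACS severity definition: "ACS is a clinical diagnosis and will be determined based on discharge diagnosis by the hematology team". Under Monitoring During Study: "A symptom questionnaire to assess for potential side effects of arginine will be completed daily by the study coordinator". The laboratory schedule in that section stops at day 7 or discharge.

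On length of stay, the rationale before Study Objectives hypothesises that arginine will help shorten it and says that ED discharge will be studied. The background reports 4.1 versus 4.8 days in the earlier single-center trial (p=0.27). Specific Aim 1 comments that "the trending decrease by 17 hours is a clinically relevant improvement for patients and their families". The length-of-stay power section considers reductions of 17 to 24 hours.

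**The concern.** A patient counts as having had ACS only if it is recorded before observation closes. If observation closes at index discharge, follow-up ends at a moment that the treatment is intended to bring forward. A patient discharged early who comes back with ACS or needs a transfusion would enter the return-visit outcome, but no text adds that event to the ACS or transfusion rate. The arm with shorter stays then has less time in which to show the event, even when the hazard is the same.

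Timing matters. The background describes the arginine nadir around a positive chest film in ACS as falling "days into the VOE admission, a pattern that differed from uncomplicated VOE", which suggests that some of these events occur in the part of the stay that earlier discharge would remove.

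Safety is a named aim, ACS and transfusion are listed secondary outcomes, and the trial is meant to inform a Phase 3 study. The earlier trial recorded ACS in 3 patients on arginine and 1 on placebo, and transfusion in 5 and 4. An unresolved signal of that kind should not be estimated over unequal windows.

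**Working it through.** **The plan's own figure.** The plan gives no power or precision for these safety rates. Its only calculation on stay is the power for a 17-hour difference: 150 per group, SDs 43 and 60 h, two-sided 5%. The standard error is √(43²/150 + 60²/150) = 6.03 h. Noncentral-t power with unequal variances is 0.8025, against 0.80251 in the table. At 24 h with 76 per group it is 0.8036, against 0.80361. The inputs on stay are therefore used as the plan uses them.

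**Inputs from the protocol**
- Earlier-trial mean stay: 4.8 d = 115.2 h (placebo) and 4.1 d = 98.4 h (arginine), a gap of 16.8 h.
- Larger gap considered: 24 h, giving 115.2 − 24 = 91.2 h.
- SDs of stay: 43 h (arginine) and 60 h (placebo).
- Patients per arm: 38.
- Earlier-trial ACS: 1/28 = 3.6% on placebo; 4/56 = 7.1% with both arms pooled. Placebo transfusion: 4/28 = 14.3%.

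**Assumptions.** The documents give neither the event risk for this trial nor the distribution of onset times. Placebo in-stay risk is varied from 3.6% to 20%. The hazard is the same in both arms. The earlier trial's mean stay stands in for time from first dose.

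**Window ratio.** 98.4/115.2 = 0.854; 91.2/115.2 = 0.792.

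**Constant hazard.** h = −ln(1 − p₀)/115.2 and p₁ = 1 − exp(−h × arginine stay). For p₀ = 7%, h = 0.00063 per hour:
- 17 h gap: p₁ = 6.01%, risk ratio 0.86, and 38 × (0.0700 − 0.0601) = 0.38 fewer events.
- 24 h gap: p₁ = 5.58%, risk ratio 0.80, and 38 × (0.0700 − 0.0558) = 0.54 fewer events.

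For p₀ from 3.6% to 20%, the ratio is 0.856 to 0.868 (0.2 to 1.0 fewer events) at 17 h, and 0.795 to 0.81 (0.3 to 1.45 fewer) at 24 h.

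**Sensitivity to timing.** Simulation with gamma-distributed stays and the SDs above:

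| Onset pattern | Ratio, 17 h | Ratio, 24 h |
|---|---|---|
| Constant hazard, p₀ 7% | 0.86 | 0.80 |
| Events only after 24 h, p₀ 7% | 0.83 | 0.75 |
| Events only after 48 h, p₀ 7% | 0.76 | 0.67 |
| Early onset, median 24 h | 0.99 | 0.96 |
| Early onset, median 48 h | 0.96 | 0.92 |
| Early onset, median 72 h | 0.94 | 0.89 |
| Early onset, median 120 h | 0.91 | 0.86 |

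At p₀ = 7% the most extreme row (after 48 h, 24 h gap) is 0.9 events per 38. At the earlier trial's placebo transfusion risk of 14.3%, constant hazard gives 0.7 (17 h) or 1.0 (24 h), and the same extreme row gives 1.7.

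**Set against chance.** At p₀ = 7% and the 17 h gap, the SD of the difference in counts between two arms of 38 is √[38 × (0.07 × 0.93 + 0.0601 × 0.9399)] = 2.1 events. Under constant hazard, the probability of a Fisher test at 5% favouring arginine is 0.6% (17 h) or 0.7% (24 h). Over all the risks tried it runs from 0.1% to 3.6%.

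**Harm that could be masked.** Under constant hazard, equal in-stay risks would hide a true hazard ratio of 115.2/98.4 = 1.17 or 115.2/91.2 = 1.26.

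**With one fixed window.** Equal hazards and equal follow-up give an expected ratio of 1.00.

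**The case against.** The strongest reply is that no in-stay limit is written. Secondary outcome 11 refers explicitly to the admission, while items 9 and 10 do not. A discharge diagnosis names the source of an ACS diagnosis rather than a time limit, and a readmission has one too. The time limits in the Aim 2 sentence might even be read as covering the whole list. A reader might infer that the plan defines all four endpoints as in-stay; it does not. Closure at index discharge is the natural reading for ACS and only an inference for transfusion, deterioration and intensive care.

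Second, post-discharge capture exists. The Adverse Events section starts collection at consent, regardless of causality, with no stated stop at discharge. Returns are followed to 30 days in every arm. This stands in part: events after discharge may well be recorded. But nothing says they enter the compared rates, and the Post-Study Procedures section limits later serious events to those possibly related to treatment.

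Third, the effect on stay is unproven (p=0.27), and the earlier trial's ACS and transfusion counts ran against arginine despite its shorter mean stay. That stands against any claim that the bias is certain to appear. It does not remove the bias if the plan's own hypothesis is true.

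Fourth, a rate could mean events per patient-day, which would remove most of the constant-hazard effect. The plan does not say so. ACS or intensive care can also prolong a stay, so dividing by days in hospital is not a clean remedy, and drawing stay independently of the event, as above, is a simplification.

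**Conclusion.** The point holds as a modest, directional weakness. Four safety endpoints are compared between arms with no common window, ACS appears to stop at index discharge, and the plan expects treatment to move discharge. If it does, the in-stay rates on arginine may be biased downward.

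The size depends on assumed baseline risk and onset timing: a risk ratio of about 0.86 (17 h) or 0.80 (24 h) under constant hazard, down to 0.76 or 0.67 if events occur only after 48 h, and 0.91 to 0.99 (17 h) with early onset. For ACS-like risks this is under one event per 38 patients. It exceeds one event only where the assumed risk is around the earlier trial's transfusion risk or higher.

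A reader might go further and infer that the arginine arms will look safer, or that a false significant safety result is likely. The documents support neither. The shift requires a stay effect that has not been shown, it is smaller than chance variation in counts this low, and a nominally significant result favouring arginine remains improbable. What is affected is the estimate carried into Phase 3 planning. The change is worth making because it is cheap.

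**What to change.** In Specific Aim 2 and secondary outcomes 9 and 10:
- Count patients with new ACS, transfusion, clinical deterioration or intensive care from first study dose to one fixed day for everyone, for example the 30 days already used for returns.
- Include events diagnosed at any return encounter, and accept an ACS diagnosis from the index or a return encounter.
- Use all randomized patients as the denominator. State how a randomized patient who receives no dose is handled, for example by starting the window at randomization.
- Report in-stay rates as a supplement. Report symptom-questionnaire findings per day observed or over a fixed early period.

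The cost is protocol wording plus some chart abstraction at return visits that are already being identified. Events treated outside the hospital network will be missed, probably about equally across arms, and a 30-day window will include some events unrelated to the index episode.

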The mechanism of action for arginine therapy during VOE is UNKNOWN, although we have shown that children are metabolically different during VOE compared to baseline with respect to the arginine metabolome. Several biochemical & cellular effects of L-Arginine administration will be evaluated in order to provide mechanistic insight into potential benefits of arginine therapy based on pre-clinical data supporting each potential mechanism. Since no single mechanism occurs in isolation, multiple mechanism are likely. Blood will be drawn, and urine will be obtained, processed and stored for future analyses at the time of presentation prior to study drug delivery (day 0), on day 1 (drawn with routine am labs 12-36 hr after initiation of study drug) and then on day of 21st dose (day 7) and/or prior to discharge (or ED discharge, whichever comes first). Exhaled NO levels will be obtained at presentation and daily in children mature enough to perform the procedure based on ATS guidelines (76), or prior to discharge in the ED for those not admitted. Additional information on important clinical outcomes will also be collected. Bloodwork for safety/toxicity monitoring will also be obtained with study blood draws (see Specific Aim #2).

Potential Mechanisms Impacted by Arginine Therapy

- **Global arginine bioavailability (GAB) and the arginine metabolome:** (arginine, ornithine, citrulline, arginase, ADMA, arginase activity/concentration, creatine, urinary arginine/amino acids).

We have established that the arginine metabolome is dysregulated in SCD (Figure 1) (2, 3), low arginine concentration is associated with VOE (4), that arginine supplementation can increase NO_x when given during VOE (5), and that arginine therapy improves clinical outcomes like pain scores & total opioid use (1). The etiology of an acute arginine deficiency during VOE is unknown. Excess renal loss of amino acids may occur during VOE, though it has never been evaluated. Urinary arginine/amino acids will be evaluated together with plasma levels. ADMA is elevated in SCD (35-37) & will impact GAB (3), and also contributes to NOS uncoupling and mitochondrial dysfunction. Recent evidence suggesting a direct role for ADMA in NOS uncoupling and mitochondrial dysfunction that is attenuated by treatment with arginine (77, 78) may be of particular interest in SCD although this paradigm has not yet been explored in hemolytic anemias. Our proposal is the first to evaluate impact of arginine therapy on the arginine metabolome, oxidative stress, hemolysis, inflammation and subsequent mitochondrial dysfunction in SCD.

- **Vasodilation: (Nitric oxide (NO); Endothelin-1 (ET-1).**

Since L-arginine is the obligate substrate for NO production, an impact on this potent vasodilator is intuitively plausible and important to investigate. Our early work demonstrated a dose-dependent impact of arginine therapy on NO_x production in SCD and VOE (4). The clinical implications of NO_x levels remain to be determined and can be effected by confounders like diet. Therefore, NO_x is not an ideal biomarker in isolation but may provide valuable data when combined with information on the arginine metabolome including arginase concentration & ADMA levels, peroxynitrite concentration and mitochondrial superoxide production. Other studies have shown that IV arginine infusions can decrease levels of ET-1 (79), a potent vaso-constrictor that may play a role in vaso-occlusive events. The ability for IV arginine to improve endothelial dysfunction was associated with elevated ADMA levels (79). Our proposal will investigate the impact of arginine therapy on both NO_x, ET-1 and ADMA. One limitation is that values of any metabolite in the plasma do not necessarily reflect levels in organ systems or distinct pools. We will

